Electroencephalogram (EEG) recorded utilized a 32-channel electrode cap (Quik-Cap Neo Net; Compumedics Neuroscan, Charlotte, NC) in conjunction with CURRY 8 Data Acquisition and Online Processing software (Compumedics Neuroscan, Charlotte, NC). Electrode positions were arranged in accordance with the extended International 10–10 System. Continuous online EEG data were initially re-referenced to the averaged signals from left and right mastoid electrodes (M1 and M2), with the AFz electrode serving as the ground reference. The electrooculogram (EOG) activity was concurrently monitored using additional electrodes positioned above and below the left-eye orbit and outer canthus of each eye. To maintain optimal recording conditions, the impedance of electrodes was diligently kept below 10 kΩ throughout the entire EEG recording period. This rigorous approach ensured the reliability and accuracy of the recorded neuro-electric signals.

Procedure

Participants were required to conduct two experiments. The first served as the baseline measurement, and the second as the research intervention. The two experiments needed to be separated by at least 7 days to avoid the possible acute influence of fitness measurements on physiological and psychological variables.

For the baseline measurement, participants first completed an informed consent form. Then, they took the Digit Span Forward and Backward test (Ryan & Lopez, 2001) and filled out demographic questionnaires, which included the Physical Activity Readiness Questionnaire (PAR-Q) (American College of Sports Medicine, 2022) and the International Physical Activity Questionnaire (IPAQ) (Hagströmer et al., 2006). The Digit Span Forward and Backward test was employed to describe other variables that might influence cognitive performance (Ryan & Lopez, 2001). The PAR-Q was used following ACSM guidelines to ensure participants had no potential risk factors for performing a single bout of exercise.

(American College of Sports Medicine, 2022). The IPAQ was used to check that participants did not have exercise habits defined as total physical activity under 150 minutes per week, following ACSM guidelines (American College of Sports Medicine, 2022; Hagströmer et al., 2006). Secondly, BMI, cardiorespiratory fitness, and 10-repetition maximum (10-RM) were assessed. Cardiorespiratory fitness was estimated using the submaximal YMCA Ergometer Test with a cycle ergometer (Corival cpet, Lode, Netherlands) (American College of Sports Medicine, 2022; Beekley et al., 2004). 10-RM was measured following National Strength and Conditioning Association guidelines (National Strength and Conditioning Association, 2016) for chest press, rowing, lat pull down, shoulder press, arm curl, leg extension, leg press, and leg curl with strength training machines (Cybex, Germany). These measurements were examined to ensure the baselines of participants were similar. Finally, all participants drew lots and were randomly assigned to three groups: group CE, AE, and reading control (RC).

For the intervention, participants first conducted a pre-test of the executive function test and concurrently collected EEG activity. Secondly, participants were instructed to perform the intervention. Finally, all participants completed a post-test of the executive function test and concurrently collected EEG activity.

Task-switching test

Task-switching test comprised six blocks, each containing 64 trials. In the initial block, participants were tasked with determining whether the stimulus (digits 1–9, excluding digit 5) within the solid-line square was greater or less than the digit 5 (AAAA...). In the second block, participants identified whether the stimulus within the dotted-line square was even or odd (BBBB...). Blocks 3–6 were characterized by an equal number of stimuli from the first and second blocks, forming an alternating-runs paradigm (AABBAA...). Mean Reaction Time (RT) for correct responses and accuracy (ACC) for the following conditions were then calculated to facilitate statistical analysis: (1) homogeneous condition (AAAA or BBBB); (2) heterogeneous condition (AABBAA...); (3) non-switch (AA or BB in the heterogeneous condition); and (4) switch (AB or BA in the heterogeneous condition).

Stroop test

Stroop test comprised four blocks, each containing 108 trials. Within these trials, three types were distinguished: neutral, congruent, and incongruent trials. The neutral trial featured a square print in red, green, and blue colors. The congruent trial presented Chinese language prints in the same colors, accompanied by corresponding words [i.e., 紅 (RED), 綠 (GREEN), or 藍 (BLUE)]. In contrast, the incongruent trial displayed Chinese language prints in different colors and words [e.g., 紅 (RED) print in blue color]. Each block included an equal distribution of 36 neutral trials, 36 congruent trials, and 36 incongruent trials. Participants received explicit instructions to respond to the color of the stimulus with both speed and accuracy. Mean response time (RT), considering only correct trials, and accuracy for each Stroop condition underwent subsequent analysis.

Exercise Intensity Measurement

An objective index of exercise intensity was heart rate (HR), measured using HR monitors (H10; Polar Electro Oy, Kempele, Finland), which were employed to gauge the exercise intensity manipulation. Participants wore an HR monitor throughout the cardiorespiratory fitness test and the intervention. Four HR indices were identified: pre-test (assessed before and after the pre-test of CF), resting (assessed after sitting quietly in a comfortable chair for 5 minutes before the intervention), intervention (assessed at 2-minute intervals during the intervention), and post-test (assessed before and after the post-test of CF).

Reference

American College of Sports Medicine. (2022). *ACSM's Guidelines for Exercise Testing and Prescription* (G. Liguori, Ed. 11th ed.). Wolters Kluwer.
<https://shop.lww.com/ACSM-s-Guidelines-for-Exercise-Testing-and-Prescription/p/9781975150181>

Bekley, M. D., Brechue, W. F., deHoyos, D. V., Garzarella, L., Werber-Zion, G., & Pollock, M. L. (2004). Cross-validation of the YMCA submaximal cycle ergometer test to predict VO₂max. *Research Quarterly for Exercise and Sport*, 75(3), 337–342.
<https://doi.org/10.1080/02701367.2004.10609165>

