## The Effect of Acute Concurrent Exercise on Executive Function: An Event-Related Potential Study

## **Statistical Analyses Plan**

The statistical analyses will be conducted using IBM SPSS Statistics (IBM Corp., Armonk, NY). A one-way ANOVA will be executed to compare the demographic data among the three groups (CE vs. AE vs. RC). A one-way ANCOVA will be performed to compare the effect of acute exercise on executive function. The pretest of the cognitive test will serve as the covariance, the independent variable will be the group, and the dependent variable will be the post-test of the cognitive test. Similarly, a one-way ANCOVA will be applied to mean P3 amplitudes.

To investigate the effects of acute exercise on heart rate (HR) and lactate levels, mixed-model ANOVAs will be employed. A 3 (Group)  $\times$  4 (Timepoint: resting HR vs. preactivity HR vs. treatment HR vs. post-activity HR) design will be used for HR, while a 3 (Group)  $\times$  3 (Timepoint: Time 1 vs. Time 2 vs. Time 3) design will be used for lactate. In cases of significant interaction effects, multiple comparisons will be conducted, and Greenhouse–Geisser-adjusted F ratios will be employed when the assumption of sphericity is violated.

For mediation analyses, the PROCESS macro by Hayes (2022) will be utilized, employing a simple mediation model (Hayes & Preacher, 2014). Dummy variables will be created, with the RC group as the reference group. The incremental area under the lactate curve will serve as the mediator, calculated by subtracting lactate concentrations at Time 1 from those at Time 2 and Time 3. The post-test of the cognitive test will be the dependent variable, and the pretest of the cognitive test will serve as the covariate. Mediation effects will be assessed through a bootstrap method (5000 resamples) with a 95% confidence interval (CI). The examination will include total effects, direct effects, regressions of group to lactate, regressions of lactate to executive function, and indirect effects, with significance determined by the 95% CI.

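### The lot is drawn before the visit that opens with the executive-function/EEG pre-test, and no sealed lot is described, so the SAP's covariate may be measured with the arm known

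*Protocol*

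**What the plan says.** The Protocol (Procedure) describes two visits: "The first served as the baseline measurement, and the second as the research intervention". On spacing it says: "The two experiments needed to be separated by at least 7 days".

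The baseline list runs through consent, Digit Span, questionnaires, BMI, fitness and 10-RM. It adds "These measurements were examined to ensure the baselines of participants were similar" and closes with "Finally, all participants drew lots and were randomly assigned to three groups: group CE, AE, and reading control (RC".

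The next paragraph begins the second visit: "For the intervention, participants first conducted a pre-test of the executive function test and concurrently collected EEG activity". Then comes "Secondly, participants were instructed to perform the intervention", followed by the post-test.

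The SAP (Statistical Analyses Plan) says of the cognitive ANCOVA: "The pretest of the cognitive test will serve as the covariance". Of the EEG outcome it says: "Similarly, a one-way ANCOVA will be applied to mean P3 amplitudes". The mediation model also has the cognitive pre-test as covariate.

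Neither document mentions sealed or opaque lots, delayed disclosure, or masking of participants or testers.

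**The concern.** A baseline covariate is most secure when it is measured before anyone can know the allocation. Here the draw is listed first and made by the participants themselves, so they may know their arm when they sit the pre-test. The tasks are scored on speed and accuracy, which depend on effort. Someone who expects to cycle, lift or read magazines might perform differently. If so, the covariate carries part of an arm effect and the adjustment moves the group comparison.

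The order has a second consequence. Anyone lost between the draw and the second visit is lost after randomisation with neither a pre-test nor a post-test. Such a person cannot enter the ANCOVA or the mediation model, and the documents do not say how these losses are reported.

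**Working it through.** The plan states no slope, shift, power or type I error calculation for this design, so there is no figure to reproduce.

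**Order of steps.** The draw may close each person's first visit, which is the more natural reading. It may instead be one joint draw after all baselines were reviewed, which the sentence on similar baselines leaves open. On both readings it is listed before the pre-test. Only on the first is the gap certainly at least 7 days.

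**When the arm is learned.** The instruction to perform the intervention fixes when participants started, not when they learned their arm. Early knowledge is possible but not stated.

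**Bias formula.** Let b be the slope of post-test on pre-test, and let knowing the arm shift one arm by δ SD. The adjusted difference is the post-test difference minus b times the pre-test difference.

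- Shift at pre-test only: 0 - bδ = -bδ
- Shift at both tests: δ - bδ = (1 - b)δ
- Shift at post-test only, as when the lot is opened after the pre-test: δ
- No shift: 0

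At δ = 0.2 and b = 0.5 / 0.7 / 0.8, the pre-test-only bias is -0.10 / -0.14 / -0.16 SD. If the shift persists it is +0.10 / +0.06 / +0.04 SD.

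**Type I error.** Assumptions: three-arm ANCOVA, no true effect, unit-variance scores with correlation b = 0.7, one arm shifted by δ = 0.2, 5% F test, 200,000 simulated trials per cell. The Protocol's recruitment figure of seven to eight is unclear, so three arm sizes are shown: 3 if it is a total (8/3 = 2.7, rounded up), 8 if it is per arm, and 26 if 78 was meant (78/3).

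| Shift | Bias (SD) | 3 per arm | 8 per arm | 26 per arm |
|---|---|---|---|---|
| None | 0 | about 5% | about 5% | about 5% |
| Pre-test only | -0.14 | 5.3% | 6.4% | 10.0% |
| Both tests | +0.06 | 5.1% | 5.4% | 5.9% |
| Post-test only | +0.20 | 5.6% | 7.7% | 15.9% |

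Repeat simulations agree to within about 0.3 percentage points. At δ = 0.4 the pre-test-only row becomes 6.2% / 10.3% / 26.7%. At 26 per arm and δ = 0.2, slopes of 0.5 and 0.8 give 6.7% and 14.7% in that row.

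**Can the data rule a shift out?** For a one-way ANOVA on the pre-test with one arm shifted, the noncentrality is n × (2/3) × δ². At δ = 0.2 this is 0.08 / 0.21 / 0.69 for 3 / 8 / 26 per arm, giving power of 5.4% / 6.4% / 10.4%.

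Dropping the pre-test from the ANCOVA adds little. The two estimates differ by the estimated slope times the observed pre-test difference. At 26 per arm that gap averages -0.14 SD with a sampling SD of about 0.7 × √(2/26) = 0.19, and it correlates about -0.99 with the pre-test difference. Replacing the pre-test with a covariate measured before the draw, assumed to correlate 0.3 with both tests, gives a correlation of -0.88.

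**Losses.** One participant lost between draw and second visit is 1/3 = 33%, 1/8 = 12.5% or 1/26 = 3.8% of an arm. No loss is documented.

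**The case against.** The strongest reply is that no error is shown. The procedure text is short, and its silence about sealed lots is weak evidence that there were none. The instruction step at the second visit is compatible with disclosure at that point. This stands. A reader might infer that participants knew their arm at the pre-test, and the documents do not say so.

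A reader might also infer that a covariate measured after randomisation makes the ANCOVA invalid. It does not. Without an arm-related shift there is no bias, and the documents give no evidence of a shift, its size or its sign.

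A third objection is that re-ordering can look worse. The arm is necessarily known at the post-test. If expectancy acts at both tests, the present order leaves 0.06 SD in the adjusted difference and the late draw leaves 0.20 SD, with rejection at 26 per arm rising from 5.9% to 15.9%. This is correct and limits what the change can be said to achieve. The absorption is accidental and depends on the slope, so it is no reason to keep the order.

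Digit Span is also a cognitive measure listed before the draw, but it is neither the outcome task nor the SAP's covariate. Losses between visits are a separate matter from arm knowledge. They belong here only because the same change of order deals with both.

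**Conclusion.** The point holds as a minor design weakness. The covariate is listed after randomisation and may have been measured with the arm known, and nothing in the documents excludes that. The evidence goes no further, and actual bias would be an inference beyond the text.

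At the arm sizes that the Protocol's wording literally allows (3 or 8), a 0.2 SD shift confined to the pre-test adds 0.3 or 1.4 percentage points to a 5% error rate (5.3 - 5.0 and 6.4 - 5.0), which is negligible. The 10.0% figure needs 26 per arm, which the documents do not state. Slope, shift and arm size are all assumptions.

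The order is still worth changing. The exercise cannot be masked, so the pre-test is the only executive-function/EEG outcome measurement that can be kept free of arm knowledge.

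**What to change.** **For any participant not yet allocated:** draw the lot, or open a sealed opaque envelope, at the second visit after the executive-function/EEG pre-test and immediately before the intervention. This protects the covariate and places losses between the visits before randomisation.

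**Where allocation is complete** (the Protocol is in the past tense): state when and to whom the arm was revealed, report losses between the draw and the second visit by arm, and name the limitation. Do not offer a pre-test comparison by arm, or an ANCOVA without the pre-test, as proof that there was no shift.

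**Cost:** a change in the order of existing steps, or a few sentences of reporting. The laboratory must be ready for all three arms on the day. Expectancy at the post-test remains and is no longer partly absorbed by the covariate, so the change must not be presented as removing expectancy bias.

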## The Effect of Acute Concurrent Exercise on Executive Function: An Event-Related Potential Study

## **Statistical Analyses Plan**

The statistical analyses will be conducted using IBM SPSS Statistics (IBM Corp., Armonk, NY). A one-way ANOVA will be executed to compare the demographic data among the three groups (CE vs. AE vs. RC). A one-way ANCOVA will be performed to compare the effect of acute exercise on executive function. The pretest of the cognitive test will serve as the covariance, the independent variable will be the group, and the dependent variable will be the post-test of the cognitive test. Similarly, a one-way ANCOVA will be applied to mean P3 amplitudes.

To investigate the effects of acute exercise on heart rate (HR) and lactate levels, mixed-model ANOVAs will be employed. A 3 (Group)  $\times$  4 (Timepoint: resting HR vs. preactivity HR vs. treatment HR vs. post-activity HR) design will be used for HR, while a 3 (Group)  $\times$  3 (Timepoint: Time 1 vs. Time 2 vs. Time 3) design will be used for lactate. In cases of significant interaction effects, multiple comparisons will be conducted, and Greenhouse–Geisser-adjusted F ratios will be employed when the assumption of sphericity is violated.

For mediation analyses, the PROCESS macro by Hayes (2022) will be utilized, employing a simple mediation model (Hayes & Preacher, 2014). Dummy variables will be created, with the RC group as the reference group. The incremental area under the lactate curve will serve as the mediator, calculated by subtracting lactate concentrations at Time 1 from those at Time 2 and Time 3. The post-test of the cognitive test will be the dependent variable, and the pretest of the cognitive test will serve as the covariate. Mediation effects will be assessed through a bootstrap method (5000 resamples) with a 95% confidence interval (CI). The examination will include total effects, direct effects, regressions of group to lactate, regressions of lactate to executive function, and indirect effects, with significance determined by the 95% CI.

